4.3.6.1. Hematological DLTs

- Grade 4 neutropenia
- Febrile neutropenia, defined as ANC $<1.0 \times 10^9/L$ [$<1000/mm^3$] with a single temperature of $>38.3^{\circ}C$ [$101^{\circ}F$], or a sustained temperature of $38^{\circ}C$ [$100.4^{\circ}F$] for more than 1 hour.
- Grade ≥ 3 neutropenia lasting >7 days;
- Grade 3 neutropenia with infection;
- Grade 4 thrombocytopenia
- Grade 3 thrombocytopenia with bleeding or requiring platelet transfusion
- Grade 4 anemia
- Grade 3 anemia requiring blood transfusion.

4.3.6.2. Non-Hematologic DLTs

Any treatment-related Grade ≥ 3 non-hematologic toxicity (see below for specifications applying to special circumstances):

- Hepatic toxicity:
 - Clinical events consistent with Hy's Law, ie,
 - ≥ 3 -fold elevations above the ULN of ALT or AST AND;
 - >2 x ULN elevation of serum total bilirubin without alternative explanation (eg, cholestasis or Gilbert's syndrome) AND;
 - Absence of initial findings of cholestasis (eg, elevated serum ALP) AND;
 - Absence of other reason(s) to explain the combination of increased AT and TBili, such as viral hepatitis A, B, or C; preexisting or acute liver disease; or another drug capable of causing the observed injury.
 - For participants with Grade 2 hepatic transaminase or alkaline phosphatase levels at baseline as a result of liver metastasis or bone metastasis, a hepatic transaminase or alkaline phosphatase level >10 times the ULN.
- Grade ≥ 3 fatigue lasting ≥ 5 days.
- Grade ≥ 3 nausea/vomiting or diarrhea lasting ≥ 3 days despite adequate antiemetic and other supportive care.
- Grade ≥ 3 CRS of any duration.
- Grade ≥ 3 QTcF prolongation (Repeat testing, re-evaluate by a qualified person, and correct reversible causes (such as electrolyte abnormalities or hypoxia). If, after

correction of any reversible causes, the Grade 3 QTcF prolongation persists, then the event should be considered a DLT).

- A treatment-related AE inducing a delay by >2 weeks in receiving the next scheduled cycle.
- Grade ≥ 3 anaphylaxis.
- Any Grade 5 AE (death) not clearly due to either the underlying disease or other etiologies.

In addition, irAEs that meet the following criteria will be considered as DLTs:

- Any Grade 4 irAE regardless of duration, any \geq Grade 4 colitis regardless of duration;
- Any Grade 3 or Grade 4 non-infectious pneumonitis regardless of duration;
- Any Grade 3 irAE, excluding colitis and pneumonitis, that does not start downgrading to \leq Grade 2 within 3 days after onset of the event despite maximal supportive care including systemic corticosteroids or dose not downgrade to \leq Grade 1 or baseline within 14 days;
- Any Grade 2 pneumonitis that does not resolve to \leq Grade 1 within 3 days of the initiation of maximal supportive care.

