Part 2C: 2L+ participants with histological or cytological diagnosis of locally advanced or metastatic TNBC showing high B7-H4 expression (see [Section 8.6.2.1](#)) who have progressed after at least 1L of SOC chemotherapy and 1 line of SOC systemic therapy (eg, chemotherapy in combination with a checkpoint inhibitor if PD-L1 positive or chemotherapy alone if PD-L1 negative/low). De novo paired pre- and on-treatment biopsies are mandatory for approximately 5 participants.

4. Participants have at least 1 measurable lesion as defined by RECIST version 1.1 that has not been previously irradiated. For Part 1 dose escalation, participants with metastatic HR+ HER2- breast cancer with non-measurable but evaluable disease may be eligible after discussion with and approval from the sponsor.
5. Participants must be able to provide archival FFPE material containing tumor that is of diagnostic quality and representative of their diagnosed malignancy or consent to undergo a fresh biopsy during screening. 10 participants enrolling in Part 2B, and 5 participants enrolling in each of Parts 2A and 2C must agree to paired pre- and on-treatment biopsies. Ability of a participant to undergo biopsy safely should be determined during screening. Exceptions that biopsies cannot be obtained due to safety risk should be discussed and approved by the sponsor.
6. Participants with HR+ HER2- advanced or metastatic BrCa must have:
 - a. Documentation of ER or PR-positive tumor ($\geq 1\%$ positive stained cells) based on most recent tumor tissue utilizing an assay consistent with local standards and ASCO/CAP guidelines ([Allison et al, 2020](#))
 - b. Documentation that tumor is HER2-negative as determined by IHC score of 0/1+ or negative by *in situ* hybridization (FISH/CISH/SISH/DISH) defined as HER2/CEP17 ratio < 2 or for single probe assessment a HER2 copy number < 4 , consistent with ASCO/CAP guidelines ([Wolff et al, 2018](#)).
7. Participants with TNBC must have documentation that tumor tissue is negative ($< 1\%$ cells with nuclear positivity) for ER and PR as well as negative for HER2 as determined by IHC score of 0/1+ or negative by ISH (FISH/CISH/SISH/DISH) defined as a HER2/CEP17 ratio < 2 or for single probe assessment a HER2 copy number < 4 , consistent with ASCO/CAP guidelines ([Wolff et al, 2018; Allison et al, 2020](#)).

Informed Consent:

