8. Capable of giving signed informed consent as described in [Appendix 1](#), which includes compliance with the requirements and restrictions listed in the ICD and in this protocol.

Other Inclusion criteria:

9. ECOG PS 0 or 1.
10. Adequate Bone Marrow Function, defined as:
 - a. ANC $\geq 1,500/\text{mm}^3$ or $\geq 1.5 \times 10^9/\text{L}$;
 - b. Platelets $\geq 100,000/\text{mm}^3$ or $100 \times 10^9/\text{L}$;
 - c. Hemoglobin $\geq 9 \text{ g/dL}$.
11. Adequate Renal Function, as follows:
 - a. Serum creatinine $\leq 1.5 \times \text{ULN}$ or estimated CrCl $\geq 50 \text{ mL/min}$ as measured or calculated using the Cockcroft Gault formula below:
 - Female CrCl = $[(140 - \text{age in years}) \times \text{weight in kg} \times 0.85] / [72 \times \text{serum creatinine in mg/dL}]$;
 - Male CrCl = $[(140 - \text{age in years}) \times \text{weight in kg} \times 1.00] / [72 \times \text{serum creatinine in mg/dL}]$;
 - b. If an estimated CrCl is believed to be inaccurate for a participant, 24-hour urine collection with actual assessment of CrCl is allowed.
12. Adequate Liver Function, defined as:
 - a. Total bilirubin $\leq 1.5 \times \text{ULN}$ unless the participant has documented Gilbert's syndrome;
 - b. AST and ALT $\leq 2.5 \times \text{ULN}$; $\leq 5.0 \times \text{ULN}$ if there is liver involvement by the tumor;
 - c. Alkaline phosphatase $\leq 2.5 \times \text{ULN}$ ($\leq 5 \times \text{ULN}$ in case of bone or liver metastasis).
13. Participants with brain metastases must meet all the following conditions:
 - a. Have completed their planned course of treatment;
 - b. Have recovered from the acute effects of radiation therapy or surgery prior to first dose;
 - c. Have discontinued corticosteroid treatment for these metastases for at least 4 weeks;
 - d. Have been on stable doses of anti-seizure medications (if applicable) for at least 3 months. Antiseizure medications must meet any eligibility criteria outlined for concomitant medications.
 - e. Are neurologically stable for 3 months since the conclusion of therapy, as documented by both neurologic and MRI examinations.

- f. Participants who are diagnosed with a CNS metastasis during the screening period must also meet these criteria.
14. Resolution of acute effects of any prior therapy to either baseline severity or CTCAE Grade ≥ 1 (except for AEs not constituting a safety risk in the investigator's judgment).

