10.6. Appendix 6: Liver Safety: Suggested Actions and Follow-Up Assessments

Potential Cases of Drug-Induced Liver Injury

Humans exposed to a drug who show no sign of liver injury (as determined by elevations in transaminases) are termed “tolerators,” while those who show transient liver injury but adapt are termed “adaptors.” In some participants, transaminase elevations are a harbinger of a more serious potential outcome. These participants fail to adapt and therefore are “susceptible” to progressive and serious liver injury, commonly referred to as DILI. Participants who experience a transaminase elevation above $3 \times$ ULN should be monitored more frequently to determine if they are “adaptors” or are “susceptible.”

In the majority of DILI cases, elevations in AST and/or ALT precede TBili elevations ($>2 \times$ ULN) by several days or weeks. The increase in TBili typically occurs while AST/ALT is/are still elevated above $3 \times$ ULN (ie, AST/ALT and TBili values will be elevated within the same laboratory sample). In rare instances, by the time TBili elevations are detected, AST/ALT values might have decreased. This occurrence is still regarded as a potential DILI. Therefore, abnormal elevations in either AST OR ALT in addition to TBili that meet the criteria outlined below are considered potential DILI (assessed per Hy’s law criteria) cases and should always be considered important medical events, even before all other possible causes of liver injury have been excluded.

The threshold of laboratory abnormalities for a potential DILI case depends on the participant’s individual baseline values and underlying conditions. Participants who present with the following laboratory abnormalities should be evaluated further as potential DILI (Hy’s law) cases to definitively determine the etiology of the abnormal laboratory values:

- Participants with AST/ALT and TBili baseline values within the normal range who subsequently present with AST OR ALT values $>3 \times$ ULN AND a TBili value $>2 \times$ ULN with no evidence of hemolysis and an alkaline phosphatase value $<2 \times$ ULN or not available.

For participants with baseline AST OR ALT OR TBili values above the ULN, the following threshold values are used in the definition mentioned above, as needed, depending on which values are above the ULN at baseline:

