- Preexisting AST or ALT baseline values above the normal range: AST or ALT values >2 times the baseline values AND $>3 \times$ ULN; or $>8 \times$ ULN (whichever is smaller).
- Preexisting values of TBili above the normal range: TBili level increased from baseline value by an amount of at least $1 \times$ ULN or if the value reaches $>3 \times$ ULN (whichever is smaller).

Rises in AST/ALT and TBili separated by more than a few weeks should be assessed individually based on clinical judgment; any case where uncertainty remains as to whether it represents a potential Hy’s law case should be reviewed with the sponsor.

The participant should return to the investigator site and be evaluated as soon as possible, preferably within 48 hours from awareness of the abnormal results. This evaluation should include laboratory tests, detailed history, and physical assessment.

In addition to repeating measurements of AST and ALT and TBili for suspected Hy's law cases, additional laboratory tests should include albumin, CK, direct and indirect bilirubin, GGT, PT/INR, total bile acids, and alkaline phosphatase. Consideration should also be given to drawing a separate tube of clotted blood and an anticoagulated tube of blood for further testing, as needed, for further contemporaneous analyses at the time of the recognized initial abnormalities to determine etiology. A detailed history, including relevant information, such as review of ethanol, acetaminophen/paracetamol (either by itself or as a coformulated product in prescription or over-the-counter medications), recreational drug, or supplement (herbal) use and consumption, family history, sexual history, travel history, history of contact with a jaundiced person, surgery, blood transfusion, history of liver or allergic disease, and potential occupational exposure to chemicals, should be collected. Further testing for acute hepatitis A, B, C, D, and E infection, liver imaging (eg, biliary tract), and collection of serum samples for acetaminophen/paracetamol drug and/or protein adduct levels may be warranted.

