All cases demonstrated on repeat testing as meeting the laboratory criteria of AST/ALT and TBili elevation defined above should be considered potential DILI (Hy's law) cases if no other reason for the LFT abnormalities has yet been found. **Such potential DILI (Hy's law) cases are to be reported as SAEs, irrespective of availability of all the results of the investigations performed to determine etiology of the LFT abnormalities.**

A potential DILI (Hy's law) case becomes a confirmed case only after all results of reasonable investigations have been received and have excluded an alternative etiology.

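### Appendix 6 has no raised-baseline ALP rule, so participants who enter with ALP of 2 to 5 × ULN cannot meet its Hy's law definition while ALP stays there

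*Protocol*

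**What the plan says.** **Entry.** Protocol 5.1, criterion 12c, allows ALP up to 2.5 × ULN in anyone and up to 5 × ULN "in case of bone or liver metastasis". Criterion 4 adds that Part 1 participants with metastatic HR+ HER2- breast cancer "with non-measurable but evaluable disease may be eligible after discussion with and approval from the sponsor". Appendix 12 classes bone disease as non-measurable, apart from measurable soft-tissue components.

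**Potential Hy's law case.** With normal baseline values, Appendix 6 asks for AST or ALT >3 × ULN and bilirubin >2 × ULN "with no evidence of hemolysis and an alkaline phosphatase value" below 2 × ULN or not available. It continues: "For participants with baseline AST OR ALT OR TBili values above the ULN, the following threshold values are used in the definition mentioned above". Two lines follow, one for AST/ALT and one headed "Preexisting values of TBili above the normal range". There is none for ALP. Potential "cases are to be reported as SAEs, irrespective of availability of all the results" of the etiology investigations.

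**Hy's law DLT.** The bullet in 4.3.6.2 requires ALT or AST at least 3 × ULN, bilirubin >2 × ULN without another explanation, "Absence of initial findings of cholestasis (eg, elevated serum ALP) AND" no other reason for the combination. It gives no multiple of ULN for ALP and does not mention baseline ALP. A separate bullet begins "For participants with Grade 2 hepatic transaminase or alkaline phosphatase levels at baseline as a result of liver metastasis or bone metastasis" and sets a limit of >10 × ULN for transaminase or ALP.

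**The concern.** Hy's law rules exist to catch a combined transaminase and bilirubin rise before its cause is known. ALP is used to set aside cholestatic cases. Raised ALP from bone metastasis is not a sign of cholestasis, and the protocol expects it: criterion 12c makes room for it and 4.3.6.2 names it.

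Appendix 6 says that its thresholds depend on each participant's baseline and underlying conditions, and it carries that through for AST/ALT and bilirubin. For ALP it does not. A participant admitted at 3 × ULN fails the ALP condition before the first dose.

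Two things are at stake. The first is liver safety reporting in both parts of the study. The expedited SAE rule and the extended panel depend on meeting the definition. GGT and direct bilirubin help to tell bone-derived ALP from cholestasis, but they are not in the routine chemistry panel (Appendix 2, Table 13). They are listed only for potential Hy's law cases, so the participants who most need them cannot trigger them. The second is consistency on DLT, a Part 1 primary endpoint, because the DLT bullet leaves the ALP judgement open.

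**Working it through.** The plan states no figure on this point, so there is nothing to reproduce. The check applies the written rules to permitted values. All values are multiples of ULN, and no hemolysis is assumed.

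**Rules used**

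- Entry ALP (5.1, 12c): ≤2.5, or ≤5 with bone or liver metastasis.
- Appendix 6, AST/ALT: >3. If baseline is raised: >2 × baseline and >3, or >8, whichever is smaller.
- Appendix 6, bilirubin: >2. If baseline is raised: a rise of at least 1, or >3, whichever is smaller.
- Appendix 6, ALP: <2 or not available, whatever the baseline.

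**Step 1. Large rises with ALP held at its entry value**

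- Case A: normal baseline; AST/ALT 10, bilirubin 6.
- Case B: baseline AST/ALT 4; AST/ALT 20, bilirubin 6. The AST/ALT limit is 2 × 4 = 8, and 20 > 8.
- Case C: baseline bilirubin 1.5; AST/ALT 10, bilirubin 6. The rise is 6 − 1.5 = 4.5, which is ≥1.

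| ALP | Eligible without bone or liver metastasis | Eligible with | A | B | C |
|---|---|---|---|---|---|
| 1.0, 1.9 | yes | yes | met | met | met |
| 2.0, 2.3, 2.5 | yes | yes | not met | not met | not met |
| 3, 4, 5 | no | yes | not met | not met | not met |

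The AST/ALT and bilirubin conditions are satisfied in every cell. The ALP condition alone decides the result. The eligible range that cannot meet Appendix 6 is 2 to 2.5 for anyone and 2 to 5 with bone or liver metastasis. It can be met again only if ALP falls below 2 or is not available.

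**Step 2. One case below Grade 3**

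Take normal baseline AST/ALT and bilirubin and a stable ALP of 3 from bone metastasis. On treatment, AST/ALT is 4.5 and bilirubin 2.8.

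- Grade: the hepatic table in 10.3.5 puts AST/ALT >3 to 5 and bilirubin >1.5 to 3 in Grade 2. The general Grade ≥3 DLT rule therefore does not apply.
- Appendix 6: 4.5 > 3 and 2.8 > 2, but 3 is not < 2. Not met. With ALP at 1.9 the same case is met.
- DLT bullet: 4.5 ≥ 3 and 2.8 > 2. The rest turns on the cholestasis condition. A reader who counts raised ALP as a finding of cholestasis scores no DLT. A reader who regards stable, bone-derived ALP as no such finding scores a DLT, provided the other conditions hold. That DLT would still not be a potential Hy's law case under Appendix 6.

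**Step 3. The >10 × ULN bullet**

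As worded, Grade 2 baseline ALP alone seems to move the transaminase limit to 10 as well. Section 10.3.5, by contrast, requires permanent discontinuation for hepatic irAEs above 5. The text does not say whether this bullet displaces the Hy's law bullet.

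**The case against.** **The DLT bullet is not tied to Appendix 6.** It does not cite the appendix, contains no 2 × ULN limit and offers ALP only as an example. Section 4.3.6 already judges worsening of a baseline abnormality by a clinically significant shift. This stands. A reader might infer that such cases are barred from being DLTs, so that a participant is replaced and a cohort moves on without the event. The documents do not support that. It requires reading the Appendix 6 cut-off into 4.3.6.2. It also relies on a separate disagreement between 4.3.6 and 9.1.1.1 over missed doses, which affects any toxicity that is not a DLT. What remains is inconsistent scoring.

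**Other safeguards apply.** For the Step 2 case managed as a hepatic irAE, 10.3.5 says to withhold treatment and monitor every 3 days. If it persists beyond 5 to 7 days or worsens, it is handled as Grade 3 to 4: permanent discontinuation, steroids and a specialist consult, with imaging and biopsy to be considered. Appendix 6 asks for closer monitoring above 3 × ULN and for sponsor review where doubt remains, although that sentence opens with rises separated in time. Section 10.3.2 lets the investigator report a medically important event as an SAE, and 4.3.6.3 allows a discretionary DLT. All of this stands and narrows the point. None of it sets an ALP rule, makes the SAE report mandatory or calls for GGT and fractionated bilirubin.

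**An ALP condition is legitimate.** With liver metastasis, raised ALP may be truly cholestatic. This stands in part. It argues for a baseline-relative rule with tests to find the source, rather than for dropping ALP.

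**Conclusion.** The point holds for Appendix 6. For participants whose ALP remains at an entry value of 2 to 5 × ULN, the potential Hy's law definition cannot be met at any level of AST/ALT and bilirubin. Its SAE rule and extended work-up are therefore not triggered. This follows from the text and needs no assumption beyond ALP staying at or above 2 × ULN.

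For the DLT bullet the fault is smaller: an undefined term that allows two scorings of the same sub-Grade-3 case.

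A reader might also infer that serious liver injury would go unnoticed. The documents do not support that, because treatment-related Grade ≥3 elevations generally remain DLTs and the hepatic irAE pathway does not depend on ALP.

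The frequency cannot be estimated. Neither document says how many participants are expected to enter with ALP of 2 × ULN or more, and the width of the eligible range is no guide to how many fall in it. The change should be made because the rule is wrong for a group that the protocol deliberately admits and the repair is short.

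**What to change.** **Appendix 6.** Add a third raised-baseline line: if baseline ALP is above the ULN, ALP does not exclude a potential Hy's law case unless it has risen from baseline by a stated factor. The sponsor's hepatic safety group should set that factor. Twice baseline would mirror the AST/ALT line, but it is an upper option: at entry ALP of 5 × ULN the limit would be 2 × 5 = 10 × ULN, so an ALP of 9.9 × ULN would count as non-cholestatic. A smaller factor or an absolute cap avoids this. State that GGT and direct bilirubin are to be used to separate bone-derived ALP from cholestasis.

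**Section 4.3.6.2.** Replace the open example with a reference to the same ALP rule. State that the >10 × ULN bullet does not override the Hy's law bullet.

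**Cost.** A few lines in two sections and no new kinds of test, since the extra tests are already listed for potential Hy's law cases. Some disease-related rises would be worked up and reported as SAEs before another cause is shown, and slightly more events may count as DLTs. Appendix 6 limits the first of these, because a case is confirmed only once other causes are excluded. The remaining conditions of the DLT bullet, including no preexisting liver disease, would still apply.

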4.3.6.3. Other DLTs

Clinically important, persistent (eg, responsible for significant dose delay) toxicities that are not included in the above criteria may also be considered a DLT following review by the investigators and the sponsor. All DLTs need to represent a clinically significant shift from baseline.

The following AEs will not be adjudicated as DLTs:

- Isolated Grade 3 laboratory abnormalities that are not associated with clinical sequelae and are corrected with supplementation/appropriate management within 72 hours of their onset.
- Grade 3 amylase or lipase elevation not associated with clinical symptoms or clinical manifestations of pancreatitis. Grade 3 endocrinopathy not controlled by hormonal replacement.

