5.2. Exclusion Criteria

Participants are excluded from the study if any of the following criteria apply:

Medical Conditions:

1. Participants with any other active malignancy within 3 years prior to enrollment. Participants with secondary malignancy that had been adequately treated, or indolent tumors that would not interfere with safety and efficacy assessments might be allowed after discussion with and approval from the sponsor.
2. Participants with advanced/metastatic, symptomatic, visceral spread, that are at risk of life-threatening complications in the short term (including participants with massive uncontrolled effusions [pleural, pericardial, peritoneal], pulmonary lymphangitis, and over 50% liver involvement). Note: Participants with indwelling

catheter for drainage, or requirement for drainage no more frequently than monthly will be allowed.

3. Clinically important (eg, 150/90 mmHg) hypertension despite optimal medical therapy.
4. Known or suspected hypersensitivity to PF-07260437 or excipients.
5. History of Grade ≥ 3 immune mediated AE (including AST/ALT elevations that were considered drug related and cytokine release syndrome) that was considered related to prior immune modulatory therapy (eg, immune checkpoint inhibitors, co stimulatory agents, etc.) and required immunosuppressive therapy within 1 year of treatment. Participants with Grade 2 hypothyroidism or hypopituitarism resulting from immunotherapy on stable hormone replacement therapy and participants with chronic adrenal insufficiency receiving doses < 10 mg/day of prednisone equivalents are eligible.
6. Prior irradiation to $> 25\%$ of the bone marrow (see [Appendix 10](#), Bone Marrow Reserve in Adults).
7. Other medical or psychiatric condition including recent (within the past year) or active suicidal ideation/behavior or laboratory abnormality that may increase the risk of study participation or, in the investigator's judgment, make the participant inappropriate for the study.

Prior/Concomitant Therapy:

8. Current use of any prohibited concomitant medication(s) or those unwilling/unable to use a permitted concomitant medication(s). Refer to [Section 6.8](#), Concomitant Therapy.
9. Therapeutic anticoagulation with high bleeding risk or active bleeding.

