Liver (hepatitis)	Continue investigational treatment.	Withhold investigational treatment; increase monitoring of LFTs; resume investigational therapeutic if labs return to baseline. If elevations persist ≥ 5 to 7 days or worsen, treat with corticosteroids, resume investigational treatment if labs return to Grade 1 or baseline.	Discontinue	Discontinue
Endocrinopathies (hypothyroidism, hyperthyroidism, adrenal insufficiency, type 1 diabetes mellitus)	Continue investigational treatment.	Continue investigational treatment.	Withhold investigational treatment. If improves to Grade 1 after treatment, resume investigational therapy.	Discontinue

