Grade 3 or Grade 4 endocrinopathies (hypothyroidism, hyperthyroidism, adrenal insufficiency, type I diabetes mellitus)	
 -Withhold study treatment -Consider hospitalization -Endocrinology consult -Start thyroid hormone replacement therapy (for hypothyroidism), anti-thyroid treatment (for hyperthyroidism), corticosteroids (for adrenal insufficiency) or insulin (for type I diabetes mellitus) as appropriate -Rule-out secondary endocrinopathies (ie, hypopituitarism / hypophysitis) 	
 -Resume study treatment once symptoms and/or laboratory tests improve to Grade ≤ 1 (with or without hormone replacement/suppression). -Continue hormone replacement/suppression and monitoring of endocrine function as appropriate.
Hypopituitarism/ Hypophysitis (secondary endocrinopathies)	
 -If secondary thyroid and/or adrenal insufficiency is confirmed (ie, subnormal serum free T4 with inappropriately low TSH and/or low serum cortisol with inappropriately low ACTH): -Refer to endocrinologist for dynamic testing as indicated and measurement of other hormones (FSH, LH, GH/IGF-1, PRL, testosterone in men, estrogens in women) -Hormone replacement/suppressive therapy as appropriate -Perform pituitary MRI and visual field examination as indicated -If hypophysitis is confirmed: -Continue study treatment if mild symptoms with normal MRI. Repeat the MRI in 1 month -Withhold study treatment if moderate, severe, or life-threatening symptoms of hypophysitis and/or abnormal MRI. Consider hospitalization. Initiate corticosteroids (1 to 2 mg/kg/day prednisone or equivalent) followed 	
 -Resume study treatment once symptoms and hormone tests improve to Grade ≤ 1 (with or without hormone replacement). -In addition, for hypophysitis with abnormal MRI, resume study treatment only once shrinkage of the pituitary gland on MRI/CT scan is documented. -Continue hormone replacement/suppression therapy as appropriate.

Endocrine irAEs		
Endocrine Disorder	Initial Management	Follow-up Management
	
by corticosteroids taper during at least 1 month
 
-Add prophylactic antibiotics for opportunistic infections
	

Other irAEs (not described above)		
Grade of other irAEs (NCI-CTCAE v5.0)	Initial Management	Follow-up Management

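### The list of events that are not DLTs exempts Grade 3 endocrinopathy that hormone replacement fails to control, which is the reverse of what the rest of the protocol implies

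*Protocol*

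**What the plan says.** Section 4.3.6.3 of the protocol introduces a list with "The following AEs will not be adjudicated as DLTs". The first bullet covers isolated Grade 3 laboratory abnormalities without clinical sequelae that are put right within 72 hours. The second covers Grade 3 amylase or lipase elevation without clinical pancreatitis, and the same bullet runs on into "Grade 3 endocrinopathy not controlled by hormonal replacement".

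Section 4.3.6.2 sets the opposite default. Its headline counts any treatment-related Grade 3 or higher event, described as "non-hematologic toxicity (see below for specifications applying to special circumstances"). Among the immune-related criteria added below it is "Any Grade 3 irAE, excluding colitis and pneumonitis, that does not start downgrading to" Grade 2 or lower within 3 days despite maximal supportive care, or does not reach Grade 1 or baseline within 14 days. Endocrinopathy is not carved out. A further bullet counts "A treatment-related AE inducing a delay by >2 weeks in receiving the next scheduled cycle".

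The DLT estimand in Section 9.1.1.1 takes its definition of a DLT from Section 4.3.6. SAP Section 2.1.1 names the same variable without listing criteria.

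**The concern.** An exemption list normally removes events that would otherwise count but are considered manageable. This entry removes the event that was not managed. A participant with, for example, Grade 3 adrenal insufficiency or type 1 diabetes that replacement does not control would be recorded as having no DLT. A participant whose Grade 3 event is controlled has no endocrine exemption and falls back on the Grade 3 or higher headline.

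The DLT indicator drives three things in Part 1: the primary estimand, the posterior overdose probability used for EWOC, and the rule in Section 4.3.5 that cuts the maximum dose step from tripling to doubling after a DLT. An error in this direction under-counts toxicity in a first-in-human study of a T-cell engager for which the protocol itself anticipates immune-related events.

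**Working it through.** **Is it an inversion?** Set the relevant rules side by side.

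- *Neighbouring exemptions (4.3.6.3):* these spare laboratory findings that are corrected and enzyme rises that are clinically silent. The endocrine entry spares the event that is not corrected.
- *Immune-related DLT rule (4.3.6.2):* failure to downgrade makes a Grade 3 event a DLT. An uncontrolled Grade 3 endocrinopathy meets that rule, and also the delay bullet if the hold lasts long enough.
- *Table 11 (6.5.3), Grade 3 endocrinopathy:* "Withhold investigational treatment. If improves to Grade 1 after treatment, resume investigational therapy". Improvement is the condition for continuing.
- *Section 10.3.5, Grade 3 or 4 endocrinopathy:* "Resume study treatment once symptoms and/or laboratory tests improve to Grade" 1 or lower, whether or not the participant is on replacement.
- *Exclusion criterion 5 (5.2)* lets in "Participants with Grade 2 hypothyroidism or hypopituitarism resulting from immunotherapy on stable hormone replacement therapy". This concerns pre-existing Grade 2 disease, so it is weaker support, but it points the same way.

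Every other rule treats control as the acceptable state. No reason is given for exempting lack of control.

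**What can one exempted event do?** The plan states no figure to reproduce, so this is an illustration.

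Inputs from the documents:
- Model (Appendix 9): logit π(d) = log α + β log(d/d*).
- Prior (Appendix 9): (log α, log β) bivariate normal, means (logit p*, 0), SDs 2 and 1, correlation 0.
- Cohorts of about 3 (4.3.5). Doses 100, 300 and 900 µg (Table 8).
- Overdosing means π(d) in [0.33, 1]. A dose is usable only if that probability is below 25% (9.3.2).
- After a DLT the step is at most doubling: 2 × 900 = 1800 µg. Otherwise it is tripling: 3 × 900 = 2700 µg.

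Assumptions, because the documents give no values for p* and d*: p* = 0.15, 0.25 or 0.33, and d* = 900 or 2700 µg. In all six settings the prior overdose probability at 100 µg is 0.05 to 0.16, consistent with the protocol's statement that the starting dose satisfies EWOC.

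Hypothetical data: 0/3 at 100 µg and 0/3 at 300 µg. At 900 µg, the one uncontrolled Grade 3 endocrinopathy is either exempted (0/3) or counted (1/3). The posterior is proportional to the prior times the product of π(d)^x (1 − π(d))^(n − x) over doses, integrated on a 1201 × 1201 grid. Each cell gives P(π(d) ≥ 0.33) as exempted → counted:

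| d* (µg) | p* | at 900 µg | at 1800 µg |
|---|---|---|---|
| 900 | 0.15 | 0.03 → 0.23 | **0.23 → 0.59** |
| 900 | 0.25 | **0.05 → 0.29** | 0.28 → 0.65 |
| 900 | 0.33 | **0.06 → 0.33** | 0.31 → 0.68 |
| 2700 | 0.15 | 0.01 → 0.10 | **0.05 → 0.32** |
| 2700 | 0.25 | 0.01 → 0.14 | **0.08 → 0.40** |
| 2700 | 0.33 | 0.02 → 0.16 | **0.11 → 0.45** |

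Bold marks a change from usable to barred. Each row has exactly one.

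At 2700 µg, the tripling step, the exempted reading passes EWOC in two settings (d* = 2700 with p* = 0.15 or 0.25: 0.15 and 0.22) and fails in the other four (0.27 to 0.43). If the event is counted, 2700 µg fails EWOC in all six, and the doubling cap excludes it as well.

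The count of one change per row depends on the settings. With d* = 300 and p* = 0.10 or 0.25, both doses change: 900 µg goes 0.05 → 0.31 and 0.07 → 0.37, and 1800 µg goes 0.17 → 0.58 and 0.21 → 0.61.

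**The case against.** The strongest reply is that Section 4.3.6.2 still makes this event a DLT, so the protocol contradicts itself rather than removing the event cleanly. It is true that no precedence is stated. But an exclusion list has a function only if it overrides the inclusion rules above it, and a site that follows the text will apply it that way. The clause allowing other toxicities to be declared DLTs does not clearly rescue the event, because the event is named on the list of those that will not be.

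Other points have some force:

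- The controlled event is not wholly without relief. A purely biochemical Grade 3 abnormality corrected within 72 hours could fall under the first bullet.
- The sentence runs on from the amylase and lipase bullet, so layout may have been lost. It could even be an inclusion criterion placed in the wrong list. On either explanation the uncontrolled event should count.
- Only Grade 3 is affected. Grade 4 immune-related events remain DLTs.
- The numbers show the effect of losing any one DLT under assumed p* and d*. Nothing in the documents says how often this event would occur within 28 or 42 days, and the technical supplement with the scenarios and operating characteristics is not among the documents reviewed.
- The Dose Level Review Committee weighs all safety data, and two clinically significant related Grade 2 or higher events also trigger the doubling cap. This limits the harm. It does not correct the DLT count, the EWOC calculation or the cap's DLT trigger.

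**Conclusion.** The concern holds. The wording exempts the worse event, against the logic of the neighbouring entries, the immune-related DLT rule and the management guidance, and the SAP does not repair it. It reads as a drafting error rather than a deliberate choice.

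Its size is one misclassified participant at a time, which is 1/3 recorded as 0/3 in a typical cohort. In all six assumed settings that was enough to change the EWOC status of either 900 or 1800 µg. Which dose changes rests on p* and d*, which the documents do not give, and on the hypothetical data. That the definition is wrong does not depend on those assumptions. Because the error under-counts toxicity in the endpoint that governs escalation, it should be corrected by amendment.

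**What to change.** In Section 4.3.6.3, change the entry to *Grade 3 endocrinopathy controlled by hormonal replacement* and give it its own bullet.

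Three smaller points in the same definition are editorial and would not justify an amendment alone, but can go in with it:

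- Copy the injection-site-reaction exemption from Section 6.8.2.4 into 4.3.6.3, since the estimand points only to 4.3.6.
- State that the immune-related bullets and the exclusion list override the Grade 3 or higher headline. At present the bullets are introduced as additions, so this is only implied.
- Give Grade 3 colitis its own line, with the classification chosen by the sponsor's clinicians. The Grade 4 colitis clause repeats the rule for any Grade 4 immune-related event, so Grade 3 colitis rests on the headline alone.

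The cost is one word removed and three lines of wording. No extra data or participants are needed.
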